2.0 Background Information

2.1 Name, Description and Intended Use of the Investigational Material

[REDACTED]
[REDACTED] The adhesive is intended for contact with intact skin for a prolonged period.

The tape is supplied non-sterile in multiple sizes and lengths. The tape does not contain any medicinal substances, biological tissues, or blood products.

[REDACTED] is a general purpose medical adhesive tape for medical applications used primarily to secure dressings, lightweight tubing, and devices to skin.

2.2 Summary of Previous Studies

The studies completed to assess the biocompatibility of [REDACTED] were selected based on the international standard ISO 10993-1: 2003 (E), Biological Evaluation of Medical Devices Part 1: Evaluation and Testing.

[REDACTED] is categorized as a surface device having prolonged contact (24 hours to 30 days) on intact skin. Tests included Cytotoxicity by MEM Elution and Agar Overlay methods per ISO 10993-5; Primary skin irritation in rabbits (24 hour contact time) per ISO 10993-10; and a Guinea Pig Maximization test using saline and sesame oil extracts of the tape per ISO 10993-10. In addition, a Human Repeat Insult Patch Test (HRIPT) was conducted (n=212) on the tape. The tape was determined to be non-cytotoxic, non-irritating, and non-sensitizing.

A toxicology risk assessment of the materials used in [REDACTED] has been completed by 3M Toxicology & Compliance Solutions, 3M Medical Department, and all materials are considered safe for human use.

During the development of [REDACTED], a total of 21 clinical studies have been conducted on various, but similar, formulations of the product and there have been no adverse events noted on [REDACTED]. There have been a total of 272 healthy adult volunteers in these trials. A number of healthy adult volunteers may have participated in more than one 3M internal clinical study. To date there have not been any studies conducted on healthy infants or children.

2.3 Risk/Benefit Summary

Tapes are considered to be low risk medical devices that are commonly used throughout healthcare and in home use, and on patients of various ages, with few problems. Potential risks to the subject include possible itch, slight discomfort during removal, erythema, and skin stripping, typically without any long-term effects. No subject is expected to endure more than slight discomfort upon removal of the tape. There are no medical benefits for a subject who participates in this study.

2.4 Investigational Material Application

The product to be tested is an investigational adhesive tape for medical use and will be used as intended. There will be no control tape for this study. Tape will be provided in 1-inch wide widths and will be applied as 1-inch by 1.5-inch strips onto the back of the subject. The tape will be allowed to remain in place for approximately 24 hours before removal. The tape will be applied and removed according to the procedures listed in Appendix 1.

2.5 GCP and Regulatory Requirements

3M does not consider [REDACTED] to be a significant risk investigational device. This study will be conducted in compliance with this protocol, GCP, and applicable state and federal regulations, including 45 CFR 160 & 164 (Authorization for Use/Disclosure of PHI), 21 CFR 812.2 [b] (Investigational Device Exemptions-Abbreviated Requirements), and 50 (Informed Consent).

2.6 Study Population

Up to 24 subjects that meet the inclusion/exclusion criteria will be enrolled in the study. During recruitment, an attempt will be made to balance the genders as much as possible. Any subjects that withdraw or are withdrawn from the study may be replaced to ensure that a total of 20 subjects complete the study. (Up to 24 total subjects are anticipated to be screened and potentially enrolled in the study to reach a final enrollment target of 20 subjects.) Subjects will be healthy infant volunteers of either gender, between the ages of 6 months and 4 years of age, and free of skin problems on the intrascapular region of the back. Refer to Inclusion/Exclusion criteria listed in Section 4.0 for more detail.

3.0 Study Objectives and Purpose

The objective of this study is to determine the relative [REDACTED]. A three-prong multidimensional evaluation consisting of expert grader, subject discomfort assessment, and laboratory assessments will be used. One pre-study visit will take place up to 7 days prior to the start of the study. The study will be conducted over two days with one tape sample applied and removed. Assessments will be taken on the final day. This is to mimic a normal tape application in health care practice. Assessments will be compared to those taken in a previous study.

4.0 Study Design

4.1 Study Type

This will be a prospective study with a multidimensional evaluation, consisting of skin assessments made by an expert skin grader, subject discomfort assessments performed by an expert discomfort grader, and laboratory assessments (hair and skin cell quantification) on the removed tapes.

4.2 Primary and Secondary Endpoints

The primary endpoint will be the change in the subject discomfort (from baseline to the final assessment) using the FLACC (face, legs, activity, cry, consolability) scale.

Secondary endpoints will be laboratory assessments (hair and skin cell quantification), skin erythema (as made by an expert skin grader), skin denudation (skin stripping), and sample lift.

These endpoints will be compared to those taken in a previous study.

4.3 Randomization and Blinding

There will be no randomization used in this study, as only 1 test sample will be evaluated.

The discomfort assessor will be observing the video recording of the subject's full anterior side.

4.4 Study Materials and Labeling

Investigational Material: [REDACTED], provided in 1-inch wide rolls.

4.4.1 Investigational Material Labeling

3M will label, package and ship the study tape to the research facility. Rolls of tape will be provided in bulk. Each investigational material bulk package will be labeled with the following minimum information:

- Study Number 05-014050
- 3M Health Care Business Group, [name]
- [REDACTED]
- Identifying lot
- Quantity of contents
- For use in study 05-014050 only.
- "Use as directed in protocol"

4.4.2 Other Materials Used in this Study

- Sterile Petri Dishes
- Digital SLR camera (provided by the study investigator)
- Digital Video camera (provided by study investigator)

4.5 Study Duration

The duration of each study subject's participation will be up to 9 days (3 visits), consisting of 1 day for subject screening, including acclimation to study staff and facility, and 2 days for material application and removal.

4.6 Study Termination/Subject Discontinuation or Withdrawal/Subject Revocation of Authorization

4.6.1 Study Termination

3M or the Investigator has the right to discontinue the study at any time for medical and/or administrative reasons. As far as possible, this should occur after mutual consultation.

4.6.2 Subject Discontinuation

The Investigator may discontinue individual subjects from the study at any time. Subjects may voluntarily withdraw from the study at any time. The Investigator will provide a written report on the appropriate CRF describing the reason for discontinuance and the date of discontinuance.

A subject who discontinues may be replaced with another qualified subject who will follow the same treatment scheme as the discontinued subject in order to finish with a minimum of 20 subjects.

4.6.3 Subject Revocation of Authorization to Use and Disclose PHI

In order to implement a valid revocation of authorization, the subject's parent or legal representative **must** make the request in writing to cyberDERM, inc., [name]. The revocation cannot stop the use or disclosure of information that has been collected prior to the revocation, which is needed to ensure complete and accurate study results and is required by law or government regulation (e.g. reporting adverse events, etc.). Revocation of an authorization may not be used to withhold normal medical care from the subject but may make the subject ineligible to receive the study treatment or care.

4.7 Investigational Material Accountability

3M requires Investigators to maintain accountability and adequate inventory security of the investigational material at all times. The Investigator or designee will:

- Complete a Confirmation of Release and Receipt of Clinical Supplies form and maintain and account for inventory on the Investigational Material Disposition form.
- Keep investigational materials in a secure storage area, accessible only to authorized individuals.
- Dispense investigational material only to subjects properly enrolled into the study.
- Return all unused investigational materials to 3M at the end of the study, or dispose of as agreed upon.

4.8 Source Data

Source data includes any original documents, data, and records where any study data is first recorded (e.g., hospital records, patient charts, laboratory notes, questionnaires, photographs, and consent forms).

For this study, paper case report forms (CRFs) will be provided by cyberDERM for each subject. All required data will be recorded in the CRFs. If study-related data are recorded for the first time directly into the CRF, then the CRF is the source document. Completed CRFs will be reviewed by the site monitor to ensure accuracy and consistency of subject data.

Any discrepancies found during CRF review are to be clarified by the Investigator or designee.

4.9 Protocol Modifications

4.9.1 Protocol Amendments

The party initiating an amendment must confirm it clearly in writing using the Amendment/Administrative Revision form. It must be signed and dated by 3M, and, in the case of a significant amendment, the Investigator. A significant amendment means one that affects the safety, rights or welfare of subjects, the scope of the investigation or the scientific quality of the study.

3M will submit protocol amendments to the Investigator for submission to the IRB for pre-approval. 3M will also notify the Investigator when a protocol amendment may be implemented (post IRB approval).

4.9.2 Protocol Deviations

A deviation is a departure from the protocol.

A protocol deviation is only for an individual subject. Protocol deviations are documented on a Protocol Deviation CRF.

Deviations that potentially affect 1) subject safety, rights or welfare, 2) data integrity or 3) compromise the statistical analysis of the study require immediate communication to 3M; the Investigator must contact the 3M study monitor within 24 hours of occurrence [contact]). A Protocol Deviation Form must be completed by the Investigator and include the type of deviation and a description of the circumstances surrounding the deviation.

Deviations which are made to protect the life or physical well-being of a subject in an emergency must be reported to the IRB within 24 hours after the Investigator learns of the occurrence.

4.10 Computerized Systems

The computer software systems that will be used to create, modify, maintain, archive, retrieve, or transmit data will be: eMatrix, SAS, Excel, Word, Outlook, and Minitab.

Electronic study documents will be stored in eMatrix.

5.0 Subject Selection

5.1 Subject Inclusion Criteria

Subjects will be infants or children of either gender who meet the following criteria:

1. Who are healthy and who have intact skin at the test site with a baseline score of 0 for erythema
2. Who are between the ages of 6 months – 4 years of age (48 months)
3. Who have a Fitzpatrick Skin Type of I, II or III
4. Whose parent or legal representative agrees to not use any products (i.e. topical medications, creams, powders or ointments) on the test sites for 24 hours prior to the study start date
5. Whose parent or legal representative agrees to sponge bathe their child during the study but agrees to not bathe their child 1 hour before each visit.
6. Whose parent or legal representative agrees to not soak the tape during a sponge bath. If the site gets wet, parent or legal representative agrees to pat their child's back dry (no rubbing).
7. Whose parent or legal representative is willing to sign the Informed Consent Form (with photo release) and HIPAA Authorization.

5.2 Subject Exclusion Criteria

Subjects who are specifically excluded from this study are subjects:

1. Who are known to be developmentally delayed
2. Who have any known allergy or sensitivity to tapes
3. Who have sunburn, skin infection or scars, moles, or other blemishes on the back that would obscure grading of the test site
4. Who have had any exposure to other topical medications, creams, powders, or ointments on the test sites 24 hours prior to the start of the study
5. Who have had a strep infection within the 2 weeks prior to the start of the study
6. Who have a history of uncontrolled diabetes, psoriasis, any active dermatitis, or recent history of dermatitis or skin reactions
7. Has participated in any study in the last 2 weeks, or are currently participating in another study, or are scheduled to participate in another study during this study period.
8. Has any other skin disorders that, in the opinion of the investigator, will interfere with the study results or will increase undue risk for the child.

5.3 Subject Assent and Parent Consent

Active written assent will not be obtained because the subjects are not of the appropriate intellectual age (i.e., typically 7 years of age and older).

The Investigator must ensure that written informed consent to participate in the investigation is obtained before including any individual as a subject in the investigation. The Investigator must provide the prospective subject's parent or legal representative sufficient opportunity to consider whether or not to participate, and minimize the possibility of coercion or undue influence. The process is designed to 1) give the subject's parent or legal representative all the information that they need, 2) ensure that the subject's parent or legal representative understands the information and 3) give the subject's parent or legal representative a chance to consider study participation. The process should permit the subject's parent or legal representative to ask questions and exchange information freely.

3M Confidential

Document Name: CLIN-PROT-ICH-US-05-327187
Clinical and Non-Clinical: CLIN-INDEX-3M-SPON-US-05-014050

Specifically, the Investigator is to explain to each subject's parent or legal representative all elements of informed consent (as specified in 21 CFR 50.25 [Appendix 11.1]). After the explanation, the parent or legal representative will voluntarily sign and date the consent form if they wish their child to participate in the study. A copy of the consent form must be provided to the parent or legal representative. A signed and dated copy of the consent form must be maintained in the Investigator study documentation file at all times.

5.4 **Subject Authorization for Use and Disclosure of Protected Health Information (PHI)**

The Investigator must ensure that written authorization for use and disclosure of protected health information is obtained before including any individual as a subject in the investigation.

Specifically, the Investigator is to explain to each subject's parent or legal representative all elements of authorization as specified in 45 CFR 164.508. After the explanation, the parent or legal representative must voluntarily sign and date the authorization form if they wish their child to participate in the study. A copy of the authorization form must be provided to the parent or legal representative. A signed and dated copy of the authorization form must be maintained in the Investigator study documentation file at all times and may be placed in the subject's medical record.

An authorization form may be combined with a consent form (i.e. compound authorization) if required by the IRB. All required elements for both informed consent and authorization must be included in a compound authorization.

6.0 **Treatment of Subjects**

See Appendix 1 (Study Schedule) for listing of procedures and assessments.

6.1 **Treatment(s) to be administered**

6.1.1 **Screening Visit (Day -7 to -2)**

- Review Inclusion/Exclusion Criteria
- Obtain parent/legal representative consent
- Obtain HIPAA authorization
- Obtain relevant infant medical history
- Acclimate subject to study staff and facility

6.1.2 **Washout (Day -1)**

- Remind parent or legal representative to refrain from applying topical medications, creams, powders, ointments, etc. on test site area of the subject.

6.1.3 **Tape Application (T0)**

- Review Inclusion/Exclusion Criteria. Ensure that subjects have not exposed their skin to topical medications, creams, powders, or ointments on the test sites.
- Verify that the subject has intact skin at the test sites with no visible erythema.

- Outline and label 1 site on the child's back, between the shoulder blades using a non-toxic permanent skin marking pen. The site on the back will be 1 inch by 1.5 inches in size. The site will be remarked on Day 2 if needed.
- Perform Expert Grader baseline assessments for erythema.
- Apply investigational tape to intrascapular region with gloved hands. The child may be seated on the parent's or legal representative's lap during sample application for ease of application. Allow to dwell for approximately 24 hours.

6.1.4 **Tape Removal (T24)**

- Before tape is removed, assess tape lift at the test site. Re-mark test site with non-toxic permanent skin marking pen if needed.
- Begin filming subject when subject is relaxed and record for approximately 2 minutes prior to removal of the tape. Include at start of video a card indicating screening number and subject number.
- Remove tape with gloved hands (continue filming). Collect the tape sample in a Petri dish. Continue filming approximately 2 minutes after tape removal. Include at completion of video a card indicating screening number and subject number. Subject discomfort assessment will be rated externally.
- Take photos and perform Expert Skin Grader assessment for erythema and skin stripping approximately 30 minutes post-removal of tape.
- Tape samples shipped to study sponsor for further laboratory analysis.

7.0 **Assessment of Efficacy**

7.1 **Efficacy Parameters**

The following efficacy parameters will be computed for each subject:

7.1.1 **Tape Lift**

- Measured prior to tape removal at T24 by an expert grader.

7.1.2 **Faces, Legs, Activity, Cry and Consolability (FLACC) Behavioral Pain Assessment**

- At T24, just prior to tape removal (for approximately 2 minutes), and following tape removal (for approximately 2 minutes), the subject will be videotaped to document their reaction at baseline, upon removal, and after removal of the tape.
- Video recordings will be sent to the 3M, where the subject's reaction will be scored by a discomfort expert (identified by 3M), using the Faces, Legs, Activity, Cry and Consolability (FLACC) Behavioral Pain Assessment. The discomfort expert will be blinded as to whether the video is from baseline or the removal of the tape.
- Video recordings will be made of the subject's full anterior side. The removal of the tape will be completed only when the infant appears to be relaxed (not anxious or stressed).

7.1.3 Skin Erythema and Skin Stripping

- Measured approximately 30 minutes after tape removal on Day 2 by an expert skin grader.

7.1.4 Hair and Skin Cell Quantification

- Measured by established techniques in 3M laboratories.

7.2 Assessment Methods

7.2.1 Lift Assessment

Lift Assessment will be taken prior to removal at T24. Lift will be assessed according to the following scale:

0 = No lift

0.5 = Corner lift only (up to four corners)

1 = 1-25% lift

2 = 26-50% lift

3 = 51-75% lift

4 = 76-99% lift

5 = Tape is missing

7.2.2 Discomfort Assessment

At T24, just prior to tape removal (for approximately 2 minutes), and following tape removal (for approximately 2 minutes), the subject will be videotaped to document their reaction at baseline, upon removal, and after removal of the tape. The video recordings will be sent to the 3M, where the subject's reaction will be scored by a discomfort expert (identified by 3M) using the Faces, Legs, Activity, Cry and Consolability (FLACC) Behavioral Pain Assessment. Video recordings will be made of the subject's full anterior side. The removal of the tape will be completed only when the infant appears to be relaxed (not anxious or stressed).

7.2.3 Laboratory Assessments

The tape sample that has been removed from each subject with gloved hands will be placed in a Petri dish and shipped to 3M for further laboratory testing, including quantifying the amount of hair and skin cells removed by the tape samples. Hair counts will be completed on each tape specimen. The skin cells will be quantified using bicinchoninic acid (BCA) colorimetric detection and protein quantification on the same tape samples. The samples will be identified by screening number and subject number. If samples fell off during the 24 hour wear, the samples will not be retrieved.

7.2.4 Expert Skin Grader Assessments

At T0 (Baseline), Expert Skin Grader Assessments of Erythema will be made prior to the first tape application. At T24, Expert Skin Grader Assessments will be made approximately 30 minutes after the tape is removed. If the sample is missing at T24, no assessment will be conducted.

3M Confidential

Document Name: CLIN-PROT-ICH-US-05-327187

Clinical and Non-Clinical: CLIN-INDEX-3M-SPON-US-05-014050

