8.0 Assessment of Safety

8.1 Safety Parameters

The principle measure of safety will be the incidence of tape-related adverse events reported during the study.

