8.2 Anticipated Events

For the purpose of this study, any signs or symptoms of expected events associated with the tape application/removal including erythema, skin stripping, itching and discomfort upon removal may or may not be coded as an adverse event based on the investigator assessment.

If any of these irritation parameters appear to be highly exacerbated, more than normally associated with use conditions in this type of population, the event will be recorded as an adverse event. This can only be determined by the investigator.

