The Investigator must promptly report an adverse device effect to the 3M study monitor. If the adverse device effect is also considered by the Investigator to be serious and/or unanticipated, the Investigator must report it to the IRB as soon as possible and within IRB requirements.

A serious AE involving a non-3M commercialized product is reported to the 3M study monitor and IRB.

If a subject has no adverse device effect during the study, the absence of such must be recorded on the CRF.

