9.0 Statistics

9.1 Data Sets Analyzed

Data obtained for all subjects that enter the study and have samples applied will be analyzed in this study.

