9.2.2 Safety Analyses

The analyses listed above for erythema, denudation, and discomfort will be carried out as the safety analyses.

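### When the tape is missing at T24 no expert skin grade is made, so a lesser irritation sign still visible there may go ungraded and need not be recorded as an adverse event

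*Combined protocol and SAP*

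**What the plan says.** All references are to the combined protocol and SAP.

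- **Grading rule.** Section 7.2.4 schedules expert skin grades at baseline and about 30 minutes after removal, then adds: "If the sample is missing at T24, no assessment will be conducted".
- **Tape loss is foreseen.** The top of the lift scale in section 7.2.1 is "5 = Tape is missing", and section 7.2.3 says that fallen samples are not retrieved.
- **The grades are safety data.** Section 9.2.2: "The analyses listed above for erythema, denudation, and discomfort will be carried out as the safety analyses". Section 9.1: "Data obtained for all subjects that enter the study and have samples applied will be analyzed in this study".
- **Principal safety measure.** Section 8.1: "The principle measure of safety will be the incidence of tape-related adverse events reported during the study".
- **Adverse-event coding of expected signs.** Under section 8.2, erythema, skin stripping, itching and discomfort on removal "may or may not be coded as an adverse event based on the investigator assessment". Recording becomes compulsory at a higher level: "If any of these irritation parameters appear to be highly exacerbated, more than normally associated with use conditions in this type of population". Only the investigator can make that judgement.
- **Other capture.** Section 8.3 requires device-related and serious events to be reported, and adds: "If a subject has no adverse device effect during the study, the absence of such must be recorded on the CRF". Appendix 1 lists recording of adverse device events at T0 and T24. Section 7.2.5 plans T24 photographs.

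**The concern.** A child whose tape falls off stays in the analysis but has no post-baseline erythema or denudation grade. The adverse-event route does not fully make up for this, because below the compulsory level the investigator may leave a visible sign uncoded. The erythema and denudation safety tables would then describe only children whose tape stayed on until T24, and an omitted grade cannot be obtained later.

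The stake is modest but not empty. Section 2.2 reports no earlier studies in healthy infants or children, section 2.3 names erythema and skin stripping among the risks, and about 20 children are planned. The rule gives up an observation that could usually be made at a visit where an expert grader is already scheduled.

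**Working it through.** The plan states no figure on this point, so there is none to reproduce. The check is a comparison of sections, followed by a calculation for scale.

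**1. What happens to a visible sign at T24 when the tape is missing**

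| Route | Where | Is the sign captured? |
|---|---|---|
| Expert grade | 7.2.4 | No |
| Compulsory adverse-event record | 8.2 | Only at the higher level, as judged by the investigator |
| Discretionary adverse-event record | 8.2, 8.3 | Possibly |
| Statement that no adverse device effect occurred | 8.3 | No; it can be true while an uncoded sign is present |
| Lift score 5 | 7.2.1 | Records the loss, not the skin |
| Photograph | 7.2.5, 6.1.4 | Unclear: 7.2.5 has no missing-tape exception, but 6.1.4 times photographs after removal |

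Section 8.2 does not tie its higher level to the 0 to 4 scores, so the documents do not show which grades could escape the record.

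**2. Expected number ungraded**

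Inputs: n = 20 completers (section 9.4). The loss rate r is an assumption, shown over a range. It is also assumed that children who lose the tape are not replaced.

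- Expected ungraded = 20r
- Chance of at least one = 1 − (1 − r)^20

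| Assumed r | Expected ungraded | Chance of at least one |
|---|---|---|
| 2% | 0.4 | 1 − 0.98^20 = 33% |
| 5% | 1 | 1 − 0.95^20 = 64% |
| 10% | 2 | 1 − 0.90^20 = 88% |
| 20% | 4 | 1 − 0.80^20 = 99% |

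**3. Effect on what the tables can say**

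Suppose that no graded child has the sign. The exact two-sided 95% upper bound with g children graded is 1 − 0.025^(1/g). With m tapes lost, the proportion over all 20 lies between 0 and m/20, the top being reached if every ungraded child had the sign.

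| Tapes lost (m) | Graded (g) | Upper bound | Range over all 20 |
|---|---|---|---|
| 0 | 20 | 16.8% | 0% |
| 1 | 19 | 17.6% | 0% to 5% |
| 2 | 18 | 18.5% | 0% to 10% |
| 4 | 16 | 20.6% | 0% to 20% |

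The loss of precision is small. The ranges in the last column express what is unknown about ungraded children; they do not measure what a later inspection would recover.

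**The case against.** The strongest defence is that the rule fits the endpoint. Erythema and denudation are secondary endpoints, graded at a fixed time after a controlled removal and compared with a previous study (section 4.2). A fallen tape has no controlled removal and perhaps no known time of loss, so that measurement does not exist. This stands as a reason to keep such grades out of the comparison. It does not explain making no graded safety observation.

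Four further points stand and limit the concern:

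- A grade of 0 taken some unknown time after the loss cannot rule out a reaction that has faded. The ranges in the last table would therefore not be closed by grading at T24.
- The protocol allows up to 24 enrolled and replacement of children who withdraw or are dropped (sections 2.6, 4.6.2 and 9.4). It does not say whether a child who lost the tape counts as a completer. If such children were replaced, 20 grades might still be reached.
- Some capture remains through section 8.3 and perhaps through the photographs in section 7.2.5.
- Section 6.1.4 describes re-marking the site before removal. If both tape and outline have gone, the exact site may be uncertain.

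A reader might also infer that section 7.2.4 contradicts the line after its denudation scale and Appendix 1, which list T24 grading without exception. The sentence reads more naturally as a specific exception to that general timing.

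**Conclusion.** The point holds in a limited form. Under section 7.2.4 an irritation sign that is still visible at a lost-tape site, but below the level that section 8.2 makes recordable, may go ungraded and need not be coded as an adverse event. At an assumed loss of 5% to 10%, without replacement, this affects 1 to 2 of 20 children. Both the loss rate and the absence of replacement are assumptions that the documents neither give nor exclude.

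Three stronger readings are not supported. A reader might infer that the safety assessment fails or that reactions will go unrecorded. The principal measure in section 8.1 is intact, the higher level of irritation must still be recorded, and the investigator may code lesser signs. A reader might infer that the tables will look too favourable. Nothing in the documents links tape loss to irritation, so the direction of any bias is unknown. Finally, the grading rule does not touch the FLACC endpoint. That a lost tape leaves no removal to film is a separate matter.

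This is a cheap improvement of low importance to a second layer of safety data.

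**What to change.** Replace the sentence in section 7.2.4 with:

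> If the sample is missing at T24, erythema and denudation are still graded and photographed at the test site as far as it can be identified, flagged as tape-missing, with the time of loss recorded if known.

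Report these grades in a separate descriptive row of the safety tables, with its own denominator. Do not pool them with the 30-minute post-removal grades, and do not use them in the comparison with the previous study.

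**Cost.** One sentence, a flag and a time-of-loss field on the CRF, and one table row. The expert grader is already scheduled at T24, so no extra visit or staff is needed.

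**Downside.** The row may hold one or two children, or none. It shows only signs present at inspection, and a 0 must carry the caveat that an earlier reaction may have faded. The change captures persisting signs; uncertainty about the response at the time of loss remains.
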